9.7.6.2 Clinical Laboratory Parameters

Descriptive statistics for clinical laboratory values (in SI units) and changes from baseline values at each assessment timepoint will be presented for each clinical laboratory parameter.

In addition, descriptive statistics for values and changes from the baseline values in conventional units at each assessment timepoint will be presented for selected clinical laboratory parameters listed in the Statistical Analysis Plan (SAP).

The number and percentage of patients who have potentially clinically significant (PCS) postbaseline clinical laboratory values will be tabulated. The criteria for PCS laboratory values will be detailed in the SAP. The percentages will be calculated relative to the number of patients with available non-PCS baseline values and at least 1 postbaseline assessment for the OLTP. The numerator will be the total number of patients with available non-PCS baseline values and at least 1 PCS postbaseline value. A supportive tabular display of patients with PCS postbaseline values will be provided, including the PID number, baseline, and all postbaseline (including non-PCS) values. In addition, a tabular display showing all AEs that occurred in patients who had PCS postbaseline clinical laboratory values will be provided.

Shift tables from baseline to end of study for clinical laboratory parameters will be presented for the following categories: low, normal, and high, which are provided by the laboratory vendor.

Patients who meet the potential Hy's Law criteria from the first dose of IP to within 30 days after the last dose of IP will be summarized. Supportive tabular displays will also be provided.

9.7.6.3 *Vital Signs*

Descriptive statistics for vital signs (eg, pulse rate, systolic and diastolic BP, body weight, oral or tympanic temperature, and body weight) and changes from baseline values at each visit and at the end of study will be presented.

Vital sign values will be PCS if they meet both the observed-value criteria and the change from baseline value criteria. The criteria for PCS vital sign values will be detailed in the SAP. The percentages will be calculated relative to the number of patients with available non-PCS baseline values and at least 1 postbaseline assessment for the OLTP or the safety follow-up period. The numerator will be the total number of patients with available baseline values and at least 1 PCS postbaseline value. A supportive listing of patients with postbaseline PCS values will be provided, including the PID number, baseline values, and postbaseline values. A listing of all AEs occurring in patients who have PCS vital sign values will also be provided.

9.7.6.4 *Electrocardiogram*

Descriptive statistics for ECG parameters (ie, heart rate, PR interval, QRS interval, RR interval, QT interval, QTcB interval, and QTcF interval) and changes from baseline values at each assessment timepoint will be presented.

The number and percentage of patients with PCS postbaseline ECG values will be tabulated for the OLTP. The criteria for PCS ECG values will be detailed in the SAP. The percentages will be calculated relative to the number of patients with available non-PCS baseline values and at least 1 postbaseline assessment for the OLTP. The numerator is the total number of patients with available non-PCS baseline values and at least 1 PCS postbaseline value. A supportive tabular display of patients with PCS postbaseline values will be provided, including the PID number, baseline values, all postbaseline (including non-PCS) values, and change from baseline. In addition, a tabular display showing all AEs that occurred in patients who had postbaseline PCS ECG values will be provided.

A shift table from baseline to the end of study in the Investigator's overall interpretation of the ECG will be presented for the following categories: normal; abnormal, not clinically significant; and abnormal, clinically significant. A tabular display showing patients with postbaseline clinically significant ECG abnormalities according to the Investigator's overall interpretation will be provided.

The number and percentage of patients with change from baseline QTc > 30 msec but not exceeding 60 msec and of patients with an increase > 60 msec will be tabulated. A supportive listing that includes the PID number, all QTc values (including change from baseline values), and all AEs will be provided for all patients who have postbaseline QTc changes > 30 msec.

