9.7.6 Safety Analyses

The safety analysis will be performed using the Safety Population, defined as all patients who receive at least 1 dose of IP during the OLTP.

The safety parameters will include AEs; clinical laboratory, vital signs, and ECG parameters; and the BPRS+, CADSS, [REDACTED].

For each safety parameter, the last assessment made before the first dose of open-label IP will be used as the baseline for *de novo* patients, and the baseline of the first lead-in study will be used as the baseline for rollover patients for all analyses of that safety parameter. Continuous variables will be summarized by number of patients and mean, SD, median, minimum, and maximum values. Categorical variables will be summarized by number and percentage of patients.

9.7.6.1 *Adverse Events*

AEs will be coded by system organ class (SOC) and preferred term using the *Medical Dictionary for Regulatory Activities*.

For rollover patients, an AE (classified by preferred term) that occurs during the OLTP will be considered a treatment-emergent adverse event (TEAE) if it was not present before the first dose of IP in the first lead-in study or was present before the first dose of IP in the first lead-in study and increased in severity during the OLTP. If more than 1 AE is reported before the first dose of IP in the first lead-in study and coded to the same preferred term, the AE with the greatest severity will be used as the benchmark for comparison with the AEs occurring during the OLTP that were also coded to that preferred term.

For *de novo* patients, an AE (classified by preferred term) that occurs during the OLTP will be considered a TEAE if it was not present before the first dose of open-label IP or was present before the date of the first dose of open-label IP and increased in severity after the first dose of open-label IP. If more than 1 AE is reported before the first dose of open-label IP and is coded to the same preferred term, the AE with the greatest severity will be used for comparison with the AEs occurring during the OLTP that were also coded to that preferred term.

An AE that occurs more than 30 days after the date of the last dose of IP will not be considered a TEAE.

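### Does the vital-sign PCS percentage in 9.7.6.3 let its numerator fall outside its denominator?

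*Protocol*

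**What the plan says.** Section 9.7.6.3 (Vital Signs) first defines the event: "Vital sign values will be PCS if they meet both the observed-value criteria and the change from baseline value criteria". The cut-offs themselves are left to the SAP. It then gives the denominator as "the number of patients with available non-PCS baseline values and at least 1 postbaseline assessment for the OLTP or the safety follow-up period", and in the next sentence the numerator: "The numerator will be the total number of patients with available baseline values and at least 1 PCS postbaseline value".

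The neighbouring sections are worded a little differently.

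- **Laboratory (9.7.6.2).** The denominator ends "non-PCS baseline values and at least 1 postbaseline assessment for the OLTP". The numerator keeps the baseline condition but names no period: "The numerator will be the total number of patients with available non-PCS baseline values and at least 1 PCS postbaseline value".
- **ECG (9.7.6.4).** The paragraph opens with "The number and percentage of patients with PCS postbaseline ECG values will be tabulated for the OLTP". Its numerator sentence is "The numerator is the total number of patients with available non-PCS baseline values and at least 1 PCS postbaseline value".

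For patients rolling over from RAP-MD-04, section 9.7.6 states that "the baseline of the first lead-in study will be used as the baseline for rollover patients for all analyses of that safety parameter". For de novo patients, baseline is the last assessment before the first open-label dose.

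**The concern.** A percentage of patients should have a numerator drawn from its denominator. Here two conditions stand only in the denominator.

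1. **Baseline status.** If some patients had a PCS baseline, they would be removed from the denominator but could still be counted as cases.
2. **Period.** In a stand-alone study, the word postbaseline would fix the period. In this one, a rollover patient's baseline lies in an earlier study, so every RAP-MD-04 value after it is literally postbaseline. A patient whose only PCS value arose in RAP-MD-04 could then be reported as a case in this study. The laboratory numerator has the same gap.

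Long-term safety is the sole objective (section 8.0), and these percentages are among its planned summaries, so the wording deserves a check.

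**Working it through.** The protocol gives no PCS rate, so there is no figure to reproduce. The check is logical, with a small illustration.

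**Baseline status.** Let x_B be the baseline value. Its change from baseline is x_B − x_B = 0. A PCS vital sign must meet the observed-value criterion and the change criterion together. With any non-zero change criterion, a baseline value can never be PCS. The non-PCS condition removes 0 patients from the denominator, and the two sentences describe the same baseline group.

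This rests on the SAP's criterion. Suppose instead the SAP classed baseline on the observed value alone. Let b be the share beyond the limit at baseline, r their later PCS rate, and p the rate in the rest. The percentage as worded would be [(1 − b)p + b·r]/(1 − b). With assumed b = 5%, r = 30%, p = 5%, that is (0.0475 + 0.015)/0.95 = 6.6%, against 5.0% with the condition in both places. The protocol does not state such a rule.

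**Period.** The table lists every type of rollover patient with an available baseline. Here, *here* means the open-label or safety follow-up period of RAP-MD-06.

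| PCS in RAP-MD-04 | Status here | In denominator | Numerator, literal | Numerator, period carried over |
|---|---|---|---|---|
| No | Not assessed | No | No | No |
| No | Assessed, no PCS | Yes | No | No |
| No | PCS | Yes | Yes | Yes |
| Yes | Not assessed | No | **Yes** | No |
| Yes | Assessed, no PCS | Yes | **Yes** | No |
| Yes | PCS | Yes | Yes | Yes |

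Two types are miscounted on the literal reading, and none once the period is carried over. The fourth row should be rare, because section 9.5.2.6 calls for vital signs at every open-label visit. De novo patients occupy only the first three rows.

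To show what the literal reading would do, assume that all patients are rollovers, all are assessed here, 5% have a PCS value here, and an independent share q had one in RAP-MD-04. The literal percentage is 1 − 0.95(1 − q):

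- q = 2%: 1 − 0.95 × 0.98 = 6.9%
- q = 5%: 1 − 0.95 × 0.95 = 9.75%
- q = 10%: 1 − 0.95 × 0.90 = 14.5%

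All of these inputs are assumed. The 26 weeks to 2 years in section 9.4.6 gives no firmer anchor: it describes how long dosing regimens are assessed in RAP-MD-04, and the interval from the lead-in baseline to entry here is not stated.

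**Which reading does the protocol support?**

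- The numerator sentence directly follows the denominator sentence, which names the period, and both define one percentage.
- The Safety Population is defined by dosing in the open-label period (9.7.1.2 and 9.7.6).
- Where lead-in data are used, the protocol says so: histories (9.3.1, 9.3.2), prior medication (9.7.4.1), the rollover baseline (9.7.6) and the pre-dose adverse-event benchmark (9.7.6.1).
- The adverse-event rule is the closest parallel. For rollover patients the reference is the state before the first lead-in dose, but the events counted are those in this study's open-label period. An earlier reference point does not bring in earlier events.
- No section says that RAP-MD-04 follow-up vital signs or laboratory values enter RAP-MD-06 tables.

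**The case for a change.** The best case for a change is that the protocol itself fixes this numerator and denominator. It leaves only the PCS cut-offs to the SAP, so the wording cannot be excused as detail deferred. Elsewhere the protocol does name its period: the ECG tabulation, newly emergent adverse events, on-therapy serious adverse events, BPRS+ and CADSS. Read against those, silence in the vital-sign and laboratory numerators could be taken as deliberate. The rollover baseline makes postbaseline ambiguous here in a way it would not usually be, and aligning the sentences would cost almost nothing.

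The textual part of this stands. The two sentences in 9.7.6.3 do not match each other, the vital-sign numerator differs from the laboratory and ECG numerators, and the laboratory numerator also leaves its period to the preceding sentence. What does not follow is that any reported percentage would be wrong. That requires a programmer to ignore the period one sentence earlier and to pool another study's follow-up data without instruction. Nor does the mismatch show which sentence should give way on baseline status. Deleting the non-PCS condition would be the wrong repair if the SAP classes baseline on the observed value, so the protocol text alone does not settle that edit.

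**Conclusion.** The inconsistency in 9.7.6.3 is a clerical one, and no change to the plan is needed. Under the section's own definition the baseline condition excludes nobody. With the period carried over from the preceding sentence, every numerator patient is in the denominator and the excess is zero.

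This rests on two assumptions: the SAP's change criterion for vital signs is non-zero and is part of how baseline is classed, and analysts confine postbaseline values to RAP-MD-06. The protocol's treatment of lead-in data elsewhere supports the second. The illustrative figures of 6.9% to 14.5% in place of 5% apply only if the second fails, and are not expected results.

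The residual risk is small. The synopsis plans descriptive statistics only, and 9.7.6.3 requires a listing of patients with PCS values showing their baseline and later values, so a miscounted patient could be identified. If the text is revised for other reasons, the numerator could be worded as a subset of the denominator over the same period, but no result depends on it.

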9.7.6.5 Other Safety Parameters

Other safety parameters comprise the BPRS+, CADSS, [REDACTED]

Descriptive statistics of actual values and change from baseline for BPRS+ total score will be presented at each assessment timepoint during the OLTP.

Descriptive statistics of actual values and change from baseline for CADSS total score will be presented at each assessment timepoint during the OLTP. CADSS total score is defined as the sum of scores for 23 subjective items.

[REDACTED]

[REDACTED]

[REDACTED]

[REDACTED]

9.7.8 Interim Analysis

No interim analysis is planned for this study.

9.7.9 Determination of Sample Size

Approximately 500 patients are expected to enter the OLTP. The study will be terminated when 100 patients have completed the 52-week OLTP.

9.7.10 Computer Methods

Statistical analyses will be performed using [REDACTED].

9.8 CHANGES IN THE CONDUCT OF THE STUDY OR PLANNED ANALYSES

Any amendment to this protocol will be provided to the Investigator in writing by the Sponsor. No protocol amendment may be implemented (with the exceptions noted below) before it has been approved by the IRB and the signature page, signed by the Investigator, has been received by the Sponsor. If the protocol is amended to eliminate or reduce the risk to patients, the amendment may be implemented before IRB review and approval. However, the IRB must be informed in writing of such an amendment, and approval must be obtained within reasonable time limits.

9.9 PROTOCOL DEVIATIONS

A *protocol deviation* is any change, divergence, or departure from the study design or procedures that is under the Investigator's responsibility and oversight (as defined by regulations) without prior written IRB approval or favorable opinion of an appropriate amendment and that does not have a major impact on the patient's rights, safety, or well-being, or on the integrity and authenticity of the study data. Deviations may include, but are not limited to, departure from inclusion/exclusion criteria, dosing, duration of treatment, failure to perform the required assessments at specified timepoints, scheduling of visits not in accordance with specifications, or patient safety. Deviating from the protocol is permitted only if absolutely necessary for the safety or clinical management of the patients and must immediately be reported to the Sponsor.

Protocol deviations must be reported to the Sponsor either verbally or electronically within 5 working days from the day of discovery.

An important protocol deviation is a form of protocol deviation that has a major impact on the patient's rights, safety, or well-being, or on the integrity and authenticity of the study data. Important protocol deviations must be reported to the Sponsor within 24 hours, if possible. The IRB must be notified within the time period dictated by the IRB associated with this study.

10.0 **STUDY SPONSORSHIP**

This study is sponsored by Naurex, Inc, an affiliate of Allergan, plc.

10.1 **STUDY TERMINATION**

The Sponsor reserves the right to terminate the study in its entirety or at a specific study center before study completion.

10.2 **REPORTING AND PUBLICATION**

All data generated in this study are the property of the Sponsor. An integrated clinical and statistical report will be prepared at the completion of the study.

Publication of the results by the Investigator will be subject to mutual agreement between the Investigator and the Sponsor and will follow the Sponsor's Standard Operating Procedure on publications.

11.0 **INVESTIGATOR OBLIGATIONS**

11.1 **DOCUMENTATION**

The Investigator must provide the following to the Sponsor before the start of the study:

- A completed and signed Form FDA 1572. If, during the course of the study, any changes are made that are not reflected on Form FDA 1572, a new Form FDA 1572 must be completed and returned to the Sponsor for submission to the FDA.
- A fully executed contract
- The curricula vitae for the Investigator and all subinvestigators listed on Form FDA 1572, including a copy of each physician's license
- A copy of the original IRB approval for conducting the study. If the study is ongoing, renewals must be submitted at yearly intervals. All subsequent modifications must be submitted and approved by the IRB, as stated in [Section 5.1](#).
- A copy of the IRB-approved ICF
- A copy of the HIPAA authorization form, or other local privacy applicable forms
- A list of the IRB members or the DHHS general assurance number
- A copy of the laboratory certifications and reference ranges
- The Investigator's Statement page in this protocol, signed and dated by the Investigator
- Financial disclosure agreement completed and signed by the Investigator and all subinvestigators listed on Form FDA 1572. The Investigator and all subinvestigators will provide an updated financial disclosure agreement to the Sponsor 1 year after the completion of the study.

11.2 **PERFORMANCE**

The Investigator must demonstrate reasonable efforts to obtain qualified patients for the study.

11.3 USE OF INVESTIGATIONAL MATERIALS

The Investigator will acknowledge that the IP supplies are investigational and as such must be used strictly in accordance with the protocol and only under the supervision of the Investigator or Subinvestigators listed on Form FDA 1572. The IP must be stored in a secured place and must be locked. At study initiation, a representative from the Sponsor will inventory the IP at the study center. The Investigator must maintain adequate records documenting the receipt and disposition of all study supplies. The Sponsor will supply forms on which to record the date the IP was received and a dispensing record in which to record each patient's use. All unused IP must be returned to the Sponsor.

11.4 CASE REPORT FORMS

All patient data relating to the study will be recorded on eCRFs to be provided by the Sponsor through the EDC system. The Investigator is responsible for verifying that all data entries in the eCRFs are accurate and correct by electronically signing the completed eCRF casebook submitted to the Sponsor. The Investigator must maintain and retain accurate documentation that supports the information entered into the EDC system for source document verification and possible regulatory inspection.

11.5 RETENTION AND REVIEW OF RECORDS

Records and documents pertaining to the conduct of this study, including eCRFs, source documents, consent forms, regulatory documents, clinical laboratory results, calibration logs, or reports (including, but not limited to, all local and central laboratory results and ECG reports), and medication inventory records in all formats (including, but not limited to, written, electronic, magnetic, and optical records, and scans, x-rays, and ECGs) must be retained by the Investigator for a period of at least 15 years after study completion unless local regulations or institutional policies require a longer retention period or otherwise notified in writing by the Sponsor.

No study records shall be destroyed without notifying the Sponsor and providing the Sponsor the opportunity to arrange long-term storage for such study records or authorizing in writing the destruction of records after the required retention period.

The Investigator must permit access to any documentation relating to the study upon request of the Sponsor or applicable regulatory authorities. If the Investigator for the study retires, relocates, or for other reasons withdraws from the responsibility of keeping the study records, custody must be transferred to a suitable alternate custodian employee of the institution or to a suitably qualified and responsible third party. The Sponsor must be notified in writing of the name and address of the new custodian in advance of the transfer.

